2.4 Safety Objectives

- ✓ The proportion of the treatment failure at 4 hours and escalation of care
- ✓ The proportion of the admission of ICU for IMV
- ✓ The proportion of adverse events

3. PATIENT POPULATION

3.1 Sample Size

Sample size calculations were done using a t-test on the primary outcome. Based on our pilot trial to obtain a power of 80% and alpha of 0.05 with a 1:1 proportion of control to intervention groups, the sample size yielded a total of 100 participants for CRS, 38 for RR, and 43 for HR. Given these sample sizes, we chose to recruit a minimum of 100 subjects. However, the final sample size was 110 patients, considering the study's longitudinal aspect (with a 10% attrition rate)

3.2 Inclusion Criteria

- ✓ Consented children aged between 1 and 24 months with a clinical diagnosis of moderate and severe bronchiolitis requiring oxygen supplementation presenting to the EUMF ED or PPU

3.3 Exclusion Criteria

- ✓ Children with mild bronchiolitis
- ✓ Those with not requiring oxygen supplement
- ✓ Those admitted to ICU for IMV
- ✓ Those who received supplemental oxygen or HFNCOT at other facilities before arrival

- ✓ Those with known comorbidity (such as congenital heart disease, chronic lung disease, neuromuscular disease, metabolic disease, and immunocompromised)
- ✓ Those with a craniofacial malformation, an upper airway obstruction, pneumothorax, or nasal trauma

3.4 Withdrawal Criteria

Consenting parents/legal guardians will be informed that they have the opportunity of withdrawing their infant/s from the study at any time with no explanation. Data generated by the drawn infant/s will be censored at the time of withdrawal. They will remain part of the study and will be analyzed by intention to treat and per-protocol approach for adherent patients to their protocol. Withdrawn children who require ongoing supplemental oxygen will receive the standard care for bronchiolitis, and no additional data will be collected after withdrawal.

[figure not shown]

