Heart rate (beat per min)†	X	X	X	X	X	X	X	X	X	
Respiratory rate (breath per min)†	X	X	X	X	X	X	X	X	X	
Arterial blood pressure (mmHg)†	X	X	X	X	X	X	X	X	X	
Clinical respiratory score†	X	X	X	X	X	X	X	X	X	
PCR	X									
Blood sample*	X									
VBG*	X			X						
Concomitant Medications	X	X	X	X	X	X	X	X	X	
Medical treatment‡	X	X	X	X	X	X	X	X	X	
Adverse event record	X	X	X	X	X	X	X	X	X	

If the patient was not discharged after 96 hours, the procedures mentioned above were continued.

†All parameters were measured during the resting of children.

*Samples were performed at any time if the clinician deemed it necessary.

Protocol No 1
Date: 10/03/2017
Revised 1: 10/03/2020
Revised 2:14/02/2021

**All children included in the study were phoned after 15 days post-discharge.

†The clinician decides to use medical treatments such as beta2 agonist, systemic steroid, and hypertonic saline.

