3.6 Enrolment/Randomisation

During the clinical and eligibility assessment, and after obtaining written informed consent, we will apply nasal cannula wall oxygen at 2 L/min if a child needs supplemental oxygen. After written informed consent, the physician assigned the participants to either St-FMOT or HFNCOT by using simple randomization. On even-numbered days, patients received the St-FMOT, while on odd-numbered days received the HFNCOT. This trial is an open study because of the inability to blind clinicians, parents, or investigators to the two interventions.

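### Section 3.4 ends all data collection when a parent withdraws a child, yet keeps the child in the intention-to-treat analysis and offers no way to permit continued use of routine records

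*Combined protocol and SAP*

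**What the plan says.** All references are to the combined protocol and SAP.

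- **Trigger (3.4).** Parents are told that "they have the opportunity of withdrawing their infant/s from the study at any time with no explanation". This is the only kind of withdrawal described.
- **Data (3.4).** The child's data "will be censored at the time of withdrawal", and "no additional data will be collected after withdrawal".
- **Analysis (3.4).** Of the same children it says: "They will remain part of the study and will be analyzed by intention to treat". Section 7.2 plans both intention-to-treat and per-protocol analyses for all outcomes. Its next sentence assigns the primary times to the per-protocol approach.
- **Care (3.4).** "Withdrawn children who require ongoing supplemental oxygen will receive the standard care for bronchiolitis".
- **15-day call.** A footnote to the Schedule of Observations and Procedures reads: "All children included in the study were phoned after 15 days post-discharge". Sections 4.2 and 6.2 describe the same call. None of the three excepts withdrawn children.
- **Adverse events (6).** All are to go on the case report form, whether or not related to the device, again with no exception.
- **Blinding (3.6).** "This trial is an open study because of the inability to blind clinicians, parents, or investigators to the two interventions".
- **Attrition (3.1 and 7.1).** The target of 100 is raised to 110 for 10% attrition, which is not split by arm or by cause.

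**The concern.** An intention-to-treat analysis needs the outcome of every randomised child. Section 3.4 promises that analysis and, in the same paragraph, gives up the data it needs for part of the follow-up. A child who leaves the study early would be in the denominator with no length of stay, no length of oxygen treatment and no later ICU or adverse event result. Section 7.2 has no rule for such a child: the Mann-Whitney test for the times makes no provision for censoring, and Fisher's exact test comes with no missing-data rule.

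Much of the loss looks avoidable. Withdrawn children who still need oxygen remain under standard care, and section 5 says the trial adds no invasive procedure or investigation beyond usual care. It is a fair inference, though not something the documents state, that vital signs, end of oxygen, ICU transfer and discharge would still be in the hospital record.

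What is at stake is bias more than power. ICU admissions and adverse events after withdrawal would not enter the safety comparison, and parents who know the assigned treatment may withdraw for reasons connected with it.

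**Working it through.** **1. The passages side by side.** For a withdrawn child, 3.4 forbids further collection. The schedule footnote, 4.2 and 6.2 require a call after discharge, and section 6 requires every adverse event to be recorded. Staff cannot follow 3.4 and these passages together.

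**2. What is lost and what is kept.** Take a child withdrawn at hour 6 (an assumed time). Scheduled readings at 1, 2 and 4 hours exist; those at 12, 24, 48, 72 and 96 hours do not.

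| Outcome | Status under 3.4 |
|---|---|
| Treatment failure at 4 hours | Known |
| HR, RR, CRS up to 4 hours | Known |
| HR, RR, CRS from 12 hours | Lost |
| Primary times (HR, RR, CRS) | Known if already reached, otherwise lost |
| Length of stay, length of oxygen treatment | Lost if discharge or weaning had not yet occurred |
| ICU admission, adverse events | Known to hour 6, lost after |
| 15-day call | Barred by 3.4, required by the footnote, 4.2 and 6.2 |

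**3. The plan's own figure.** 100 × 1.10 = 110, as stated. Dividing instead, 100 / (1 − 0.10) = 111.1, or 112 with equal arms. The two are close. Planned attrition is 0.10 × 110 = 11 children, leaving 99. Attrition can have other causes, so 11 is an upper planning figure for withdrawals.

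**4. Power.** The documents give no effect size. A two-sided two-sample t-test at 5% with 80% power and 50 per arm implies a standardised CRS difference of about 0.57. At that difference, power is 83.7% with 55 v 55, 79.6% with 50 v 49 and 79.1% with 55 v 44. The loss is small and already planned for.

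**5. Worst-case range for a binary outcome.** Let e₁ and e₀ be the observed events, and m₁ and m₀ the children without an outcome, with 55 per arm.

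- Largest risk difference: (e₁ + m₁)/55 − e₀/55
- Smallest risk difference: e₁/55 − (e₀ + m₀)/55
- Width: (m₁ + m₀)/55

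The width does not depend on how the missing children split between arms.

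| Children without the outcome | Width (percentage points) |
|---|---|
| 11 | 11/55 = 20.0 |
| 4 | 4/55 = 7.3 |
| 2 | 2/55 = 3.6 |

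**6. Illustration of bias (assumed rates).** Suppose the true rate of an adverse outcome is equal in the two arms, and the children lost all come from one arm and all would have had the event. Analyse only the children with data.

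| True events per arm | Lost | Full arm | Depleted arm | Odds ratio |
|---|---|---|---|---|
| 6/55 | 4 | 10.9% | 2/51 = 3.9% | (2/49)/(6/49) = 0.33 |
| 11/55 | 4 | 20.0% | 7/51 = 13.7% | (7/44)/(11/44) = 0.64 |
| 11/55 | 6 | 20.0% | 5/49 = 10.2% | (5/44)/(11/44) = 0.45 |
| 16/55 | 4 | 29.1% | 12/51 = 23.5% | (12/39)/(16/39) = 0.75 |

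The true odds ratio is 1 in every row. These are deliberately extreme cases that show possible size only; the documents give neither event rates nor withdrawals by arm.

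**The case against.** The case on the other side has five parts.

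- **Scope of 3.4.** It covers withdrawal from the study. A reader might infer that a child whose parents only want the device stopped is discarded as well. The text does not say that. Planning a per-protocol analysis alongside intention to treat suggests that non-adherent children stay in with data. What stands is that 3.4 is silent on such families and gives them no stated way to keep contributing records.
- **Children who do not improve.** A reader might expect most of them to disappear through withdrawal. Section 5.3 gives them defined routes (failure at 4 hours, escalation, rescue, ICU), which are trial outcomes and do not trigger 3.4. This narrows the bias route to events after a parental withdrawal.
- **Differential loss.** A reader might infer that the loss is selective by arm. Open treatment makes that possible, but no document shows it.
- **Usable data.** A reader might conclude that intention to treat is impossible. That goes too far. Readings before withdrawal are kept, and the mixed models for HR and RR can use them under a missing-at-random assumption.
- **Parents' rights and consent text.** Where parents refuse further data use, collection should stop. The consent text is not in the public copy and may already offer continued use of records. Even so, 3.4 as written would bar the collection.

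The conflict with the 15-day call could be read as a general footnote giving way to a specific rule. That is a fair reading, but sections 4.2, 6 and 6.2 carry no exception either, so a clarifying clause is still needed.

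**Conclusion.** The point holds as a gap in what is collected. Section 3.4 is an explicit rule, not an omission, and following it removes post-withdrawal outcomes and harms from an analysis that is meant to include those children.

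Its size depends on the number of withdrawals, which is unknown. The 20-point width is the ceiling, reached only if all planned attrition is withdrawal and all of those children lack the outcome; a handful of withdrawals gives the smaller widths. Outcomes already recorded, such as failure at 4 hours for a child withdrawn later, are unaffected. Whether the loss would favour either arm cannot be judged from the documents. That the missing items could be recovered rests on the inference that the ward keeps them.

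The change should be made because it is cheap and prevents missing data that no later analysis can fully repair. The documents do not support calling the trial's comparison biased on this account.

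**What to change.** In 3.4, distinguish two cases:

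1. **The family stops the assigned treatment or the study procedures but permits data use.** Continue to take HR, RR, SpO₂, end of oxygen, ICU admission or IMV, discharge time and adverse events from the hospital record. Continue CRS where the parent agrees. Make the 15-day call.
2. **The family refuses further data use.** Stop collection from that moment and keep what was recorded before it.

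Record the date, hour and type of each withdrawal, and the reason if the parent offers one, since none is required. Add a sentence to the schedule footnote and to sections 4.2, 6 and 6.2 saying how each applies in the two cases, so that they agree with 3.4. Report withdrawals by arm and type.

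The cost is a short amendment to the protocol and consent form (if the consent form does not already cover this) and chart abstraction for at most about 11 children. Clinical care is not changed.

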3.5 Participant selection

Children aged between 1 and 24 months with moderate and severe bronchiolitis requiring oxygen supplementation presenting to the EUMF ED or PPU with parents/legal guardians' informed consent will be randomized to experimental (HFNCOT) or standard oxygen therapy (St-FMOT).

3.6 Enrolment/Randomisation

During the clinical and eligibility assessment, and after obtaining written informed consent, we will apply nasal cannula wall oxygen at 2 L/min if a child needs supplemental oxygen. After written informed consent, the physician assigned the participants to either St-FMOT or HFNCOT by using simple randomization. On even-numbered days, patients received the St-FMOT, while on odd-numbered days received the HFNCOT. This trial is an open study because of the inability to blind clinicians, parents, or investigators to the two interventions.

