7.3 Statistical Analysis Plan.....	21
8. REGULATORY CONSIDERATIONS.....	21
8.1 Participant Consent.....	22
8.2 Ethical Review.....	22
8.3 Sponsor.....	22
9. STUDY ADMINISTRATION.....	22
9.1 Protocol Deviations.....	22
9.2 Monitoring and Auditing.....	23
9.3 Study Documentation and Records Retention.....	23
9.4 Publication and Use of Study Findings.....	24
10. APPENDICES.....	25
11. REFERENCES.....	33

ABBREVIATIONS

AE	Adverse event
CI	Confidence interval
CPAP	Continue positive airway pressure
CRF	Case report form
CRS	Clinical respiratory score
ED	Emergency department
EUMF	Ege University Medical Faculty
FiO ₂	Fraction of inspired oxygen
FLUA	Influenza A
HR	Heart rate
HREC	Human Research Ethics Committee
HFNCOT	High-flow nasal cannula oxygen treatment
HRV	Human rhinovirus
IMV	Invasive mechanical ventilation
IND	Investigational new drug
IPPV	Intermittent positive pressure ventilation
LOS	Length of hospital stay
LOOT	Length of oxygen treatment
MD	Mean difference
NICE	National Institute for Health and Clinical Excellence
mPCR	Multiplex polymerase chain reaction
PEEP	Positive end-expiratory pressure
PEWS	Pediatric early warning score
ICU	Intensive care unit
PPU	Pediatric Pulmonology Unit
RCT	Randomised controlled study
RR	Respiratory rate
RSV A/B	Respiratory syncytial virus
SO ₂	Peripheral oxygen saturation
SOT	Standard oxygen treatment
St-FMOT	Standard face mask oxygen treatment
USA	United States of America
VBG	Venous blood gases

DEFINITIONS

Children

- ✓ In this study, is a child under the age of 24 months

Moderate and Severe bronchiolitis

- ✓ Defined as per CRS reported by Liu and colleagues (Appendices 1)
- ✓ Mild bronchiolitis: 0-4 point
- ✓ Moderate bronchiolitis: 5-8 point
- ✓ Severe bronchiolitis: 9-12 points

Supplemental Oxygen Requirement

- ✓ Peripheral capillary oxygen saturation (SpO_2) $<92\%$ while breathing room air

Standard Face Mask Oxygen Treatment (St-FMOT)

- ✓ The gas flow between 6.0 and 10.0 L/min

Rescue Treatment for St-FMOT

- ✓ First-tier, HFNCOT (2 L*kg/min) in the general ward
- ✓ Second-tier, admission to ICU for IMV

High-Flow Nasal Cannula Oxygen Treatment (HFNCOT)

- ✓ The gas flow at 2 L*kg/min or maximum 25 L/min

Rescue Treatment for HFNCOT

- ✓ Admission to ICU for IMV

STUDY SYNOPSIS

Title Comparison of high-flow nasal cannula and standard face mask oxygen therapy in children with moderate and severe bronchiolitis: A randomized controlled trial.

Trial Registry NCT04245202

Study Objectives

A. Primary Objectives

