- ✓ To evaluate the effect on HR, RR, and CRS
- 1. The time it takes for HR to reach its normal range for age (hour)
- 2. The time it takes for RR to reach its normal range for age (hour)
- 3. The time it takes for CRS to regress from severe [scores of 9-12] to moderate [scores of 5-8] bronchiolitis, or from moderate [scores of 5-8] to mild [scores of 0-4] bronchiolitis (hour)

B. Secondary Objectives

- ✓ The decrease in HR compared with the baseline value
- ✓ The decrease in RR compared with the baseline value
- ✓ The decrease in CRS compared with the baseline score
- ✓ The effect on LOS and LOOT

C. Safety Objectives

- 1. The proportion of treatment failure at 4 hours or escalation of care
- 2. The proportion of admission to ICU for IMV
- 3. The proportion of adverse event

Rationale

- ✓ There has been insufficient RCT conducted on children with moderate and severe bronchiolitis requiring oxygen therapy in the general ward.

Study Population

A. Inclusion Criteria

- ✓ Children aged between 1 and 24 months with moderate and severe bronchiolitis requiring oxygen supplement.

B. Exclusion Criteria

- ✓ Children with mild bronchiolitis
- ✓ Those with not requiring oxygen therapy
- ✓ Those admitted to ICU for urgent IMV
- ✓ Those who received supplemental oxygen or HFNCOT at other facilities before arrival

- ✓ Those with known comorbidity (such as congenital heart disease, chronic lung disease, neuromuscular disease, metabolic disease, and immunocompromised)
- ✓ Those with a craniofacial malformation, an upper airway obstruction, pneumothorax, or nasal trauma

Study Design

- ✓ Open-label, two-arm, phase 4 randomized controlled trial

Sample size (each group)

- ✓ 55 in each group (HFNCOT and St-FMOT)

Investigational treatment:

- ✓ Fisher & Paykel MR850 with Optiflow™ Junior Nasal Cannula System

Control Group

- ✓ St-FMOT

Duration of Treatment

- ✓ From admission to EUMF Pediatric Hospital to at 15 days of post-discharge

Centre/s

- ✓ Single-center – EUMF/Pediatric Hospital

Statistical Methods

- ✓ Chi-Squared Test, Fisher's Exact Test, Mann-Whitney-U Test, Linear Mixed Model, Bruner Langer Method

SCHEDULE OF OBSERVATIONS AND PROCEDURES

Diagnosis bronchiolitis	Screening ED or PPU	1h	2h	4h	12h	24h	48h	72h	96h	Phone follow-up
Inclusion/Exclusion criteria	X									X**
Informed consent	X									
Medical History	X									
Physical exam	X	X	X	X	X	X	X	X	X	
Bodyweight and length	X									
Body temperature (°C)	X	X	X	X	X	X	X	X	X	

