1.2 High-Flow Nasal Cannula Oxygen Delivery

Warmed humidified titrated medical air/oxygen is delivered through a non-sealing nasal cannula. The Optiflow™ system manufactured by Fisher & Paykel allows humidified flows of up to 25 L/min to be given. There is wide variation in the flows used and methods used to calculate them; however, flows are more remarkable than the standard maximum of 2 L/min. Those who exceed the patient's tidal volume are usually described as high flow. The effective delivery of high-flow oxygen at optimal humidity with dead space flushing and an element of positive airway pressure is expected to be beneficial in managing acute bronchiolitis.⁵ Previously published studies showed that HFNCOT notably decreases in HR and RR relative to St-FMOT.¹⁰⁻¹² In contrast, it was illustrated that children

treated with HFNCOT had identical results in reducing the HR and RR compared with those treated with St-FMOT.^{4,13} Otherwise, there are conflicting results in the literature regarding whether HFNCOT decreases CRS compared with SOT. Some prospective trials^{14,15} did not show a considerable reduction when comparing between HFNCOT and SOT.

In contrast, others showed that HFNCOT is more effective in reducing CRS than SOT.^{16,17} High-flow oxygen has been found to lower intubation rates and decrease the LOS for children in ICU settings.^{6,13} The Schibler et al.⁶ study followed the introduction of high-flow oxygen for bronchiolitis and found intubation rates dropped from 37% to 7% over four years as usage increased from use in 13% of patients to 66% by 2009. This RCT aims to address the gap in knowledge by studying the Fisher & Paykel® humidification system with Optiflow nasal prongs used in the care of children aged between 1 and 24 months with moderate and severe bronchiolitis requiring oxygen supplementation. Bronchiolitis was selected as there is a significant disease burden in this age group due to a variety of viral causative organisms, and no other effective medical treatment may confound results.

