1.3 Study Design Rationale

This study includes a single site longitudinal observational cohort study [HREC (03.14.2017/No: 17-2.1/18)] nested within an open, two-arm randomized control trial HFNCOT compared to St-FMOT in the management of moderate and severe bronchiolitis requiring oxygen supplementation in children aged between 1 and 24 months.

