7.2 Data Analysis Methods

Categorical and continuous variables will be expressed as frequency (percentage) and median (IQR). Between groups, we will use the Mann-Whitney-U test for comparing the time of success for HR, RR, and CRS (SPSS Inc., version 25.0, Chicago, IL, USA). The longitudinal analysis part of the study will be performed non-parametrically with the Brunner Langer model for CRS conducted with a linear mixed model in a parametric way for HR and RR. Brunner Langer model (F1-LD-F1) is applied using web-based software (R software, version 3.5.2, package: nparLD, R Foundation for Statistical Computing, Vienna, Austria; <http://r-project.org>). The PROC MIXED procedure in the SAS software is used (Version 9.3; SAS Institute, Cary, NC, USA) to perform linear mixed models in which subjects will be included as random effects. When there is a significant interaction effect in the longitudinal analysis ($P < .1$), the time effect will be analyzed in each group, and groups will be compared at baseline and following time points (the baseline was subtracted from these time points). The proportions of the treatment failure at 4 hours, rescued patient, ICU admission, and AE are analyzed using Fisher's Exact test and given with odds ratio (OR) and 95% Confidence Interval (CI). We will perform intention-to-treat and per-protocol approaches for all outcomes. The time of success for HR, RR, and CRS outcomes will be analyzed using the PP approach. A 2-sided $P < .05$ defines statistical significance.

Statistical Analysis Plan

The biostatistician in the study, which has blinded to allocation, will perform the analysis. An interim analysis will not be performed. If substantial evidence of increased risk of harms ($p < 0.001$) observed in both groups, stopping rules will be used with the biostatistician's advice. Intention to treat and per-protocol approaches will be conducted if necessary.

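### Section 3.6 calls allocation by odd or even calendar date simple randomization, but the rule has no random element and the arm is foreseeable before consent

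*Combined protocol and SAP*

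**What the plan says.** Section 3.6 says that, after written consent, "the physician assigned the participants to either St-FMOT or HFNCOT by using simple randomization". The next sentence gives the whole method: "On even-numbered days, patients received the St-FMOT, while on odd-numbered days received the HFNCOT". The same section says that clinicians, parents and investigators cannot be blinded.

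The randomized label appears in these other places:

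- Synopsis, title: "children with moderate and severe bronchiolitis: A randomized controlled trial"
- Synopsis, study design: "Open-label, two-arm, phase 4 randomized controlled trial"
- Section 1.2: "This RCT aims to address the gap in knowledge"
- Section 1.3: "open, two-arm randomized control trial HFNCOT compared to St-FMOT"
- Section 3.5: "will be randomized to experimental (HFNCOT) or standard oxygen therapy (St-FMOT"

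For the primary outcomes, section 7.2 says: "Between groups, we will use the Mann-Whitney-U test for comparing the time of success for HR, RR, and CRS". It names no covariates for that comparison. No section available for review describes a random sequence, a concealment step or an independent person who assigns.

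**The concern.** Two adjoining sentences of section 3.6 contradict each other. A calendar rule contains no chance mechanism, so the first sentence names a method that the second does not describe.

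Assigning after consent would protect the comparison only if the arm were unknown until then. Here the date shows it in advance. Staff who know that today is a face-mask day or a high-flow day can know it while they score the child, decide whether to approach the parents, and explain the study.

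The causal claim is at stake. A reader told that the trial was randomized will credit the design with protection against selection that this allocation does not give. If children enrolled on odd and even days differed in prognosis, the primary analysis would attribute the difference to treatment.

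**Working it through.** **1. The plan's own figures.** No figure in the plan describes the allocation. The nearest are the 1:1 ratio and the total of 110, 55 per arm. Adding 10% to 100 gives 100 × 1.10 = 110, as stated. Dividing by 0.90 gives 111.1, or 112 in two equal arms. The point does not depend on this difference, and the fix leaves the sample size unchanged.

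**2. Is the rule random?** From section 3.6, P(HFNCOT | odd day) = 1 and P(HFNCOT | even day) = 0. Under simple 1:1 randomization both would be 0.5. The chance of naming the next arm correctly is therefore 1 rather than 0.5.

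**3. Is day parity itself unbalanced?** In a 365-day year, seven months have 16 odd and 15 even dates, four have 15 and 15, and February has 14 and 14.

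- Odd: 7 × 16 + 4 × 15 + 14 = 186
- Even: 7 × 15 + 4 × 15 + 14 = 179

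The odd share is 186/365 = 51.0%, so about 56 of 110 children would be expected on HFNCOT if enrolment were even across days. That is trivial. The defect is foreseeability, not imbalance in numbers.

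**4. Where could foreknowledge act?** Entry needs an oxygen saturation below 92% on room air and a CRS of at least 5 (Definitions). Saturation is measured. Of the four CRS items in Appendix 1, respiratory rate is counted, while retraction, dyspnea and wheeze are graded by an observer. Which families to approach is also a judgement. The room for steering is limited but not closed.

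**5. Does the analysis correct for it?** The Mann-Whitney test uses the times alone. Section 7.2 does subtract baseline, but only in the longitudinal HR, RR and CRS comparisons that follow a significant interaction. It does not do so for the primary times to success.

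**6. Illustration only.** The documents give no size for any steering. Assume no treatment effect and a prognosis shift of s SD between arms. For a two-sided 5% z-test with 55 per arm, the non-centrality is s/√(2/55) = s/0.1907. For s = 0.10, 0.20 and 0.30 this is 0.52, 1.05 and 1.57, with rejection rates of 8.2%, 18.2% and 35.0%. Simulating the Mann-Whitney test on continuous times (20,000 trials per setting) gives 8.0%, 17.1% and 32.7%, and 5.0% at zero shift. Any test rejects more often when a shift is put in. These figures are not evidence about this trial.

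**7. What form must an adjustment take?** CRS success is a fall of one category: 9–12 to 5–8, or 5–8 to 0–4. The points needed are:

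| Starting CRS | 5 | 6 | 7 | 8 | 9 | 10 | 11 | 12 |
|---|---|---|---|---|---|---|---|---|
| Points to next category | 1 | 2 | 3 | 4 | 1 | 2 | 3 | 4 |

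Distance to success rises, drops and rises again, so a linear CRS term would misfit this outcome. CRS also cannot stand in for baseline RR in the RR outcome, because its RR item is banded, capped at 3 points and summed with three other items.

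**The case against.** The best defence is that date parity has no evident link to how ill a child is. If staff enrolled every eligible child regardless of the day, the arms could be as comparable as under true randomization. Oxygen need is measured, and two of the three primary outcomes are times to a normal vital sign. Only enrolment that depends on arm and is also related to prognosis would bias the comparison. All of this stands. It limits what can be claimed about bias, but it does not make the rule random or concealed.

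A reader might go further in four ways that the documents do not support:

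- **That steering occurred, or that the type I error is a particular figure.** No enrolment or baseline data are given, and the rates in step 6 rest wholly on assumed shifts.
- **That the deciding date is hopelessly ambiguous.** Section 3.6 places assignment after consent, so the day of assignment is the natural reading. The study-schema figure is not available and may settle it. A count of children crossing midnight would need assumed delays and arrival patterns. A one-line confirmation is enough.
- **That the biostatistician's blinding failed.** The case report form carries a date and a study-device field, but no section says that the analyst receives either. That is a separate matter.
- **That the plan ignores baseline altogether.** It uses baseline in the longitudinal comparisons, though not for the primary times.

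**Conclusion.** The concern holds in this form. The stated method is not simple randomization, and the randomized label is wrong wherever it rests on that method. Allocation is unconcealed: the arm is foreseeable with probability 1 instead of 0.5. Arm- and prognosis-dependent enrolment is possible but not shown, and the unadjusted primary comparisons would not correct for it. The size of any bias cannot be stated from the documents.

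The conclusion rests on the text of section 3.6 alone and on no numerical assumption. The missing schema could clarify the deciding date, but it could not make a calendar rule random. The correction is essential because the label carries the trial's causal claim.

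**What to change.** 1. **Relabel.** Delete the term simple randomization from section 3.6. Describe the trial as quasi-randomised, with allocation by odd/even calendar date, in the title, the synopsis and sections 1.2, 1.3, 3.5 and 3.6. Confirm that the deciding date was the day of assignment after consent, or state which date was used. Limit causal wording accordingly.
2. **Report.** Give baseline age, HR, RR and CRS by arm. Where logs exist, give screened, eligible, declined and enrolled counts by day parity.
3. **Add a sensitivity analysis** beside each Mann-Whitney result, in the same analysis sets. Use a time-to-event model suited to tied times on the visit grid, for example a discrete-time complementary log-log model. Adjust for age and baseline HR in the HR outcome, and for age and baseline RR in the RR outcome. In the CRS outcome, adjust for age, starting category and points needed to reach the next category. Prespecify how the analysis treats withdrawal, rescue HFNCOT, ICU transfer and discharge before success. State that adjustment removes only measured imbalance.
4. **Only if enrolment is still open,** replace the date rule with a concealed computer-generated sequence, released after consent and baseline scoring.

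**Cost.** The past tense in sections 3.6 and 7.1 suggests that allocation is complete, although section 3.5 uses the future. If it is complete, the cost is text changes, one baseline table and 3 outcomes × 2 analysis sets = 6 adjusted fits, with no new patients. The baseline variables are on the case report form. The form has no field for screened or declined children or for withdrawal time, so screening counts depend on separate logs. Censoring would fall at the last completed visit unless withdrawal time is held elsewhere. The price is a weaker design label and a little more analysis. If enrolment is open, add an ethics amendment, a concealed list and both devices available every day.
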